### 15G.1 Alcohol: Additional Section (Not a part of LS7 scoring)

15G.1. Have you had anything alcoholic to drink in the last 12 months?

- Yes  No

15G.2. If yes, total years of alcohol consumption.

---

15G.3. Which of the following best describes how often you CURRENTLY drink alcohol?

- Less than 1 drink a day (occasional)  
 1-2 drinks a day  
 3 or more drinks a day

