### 3.5 CASE RECORD FORMS AND QUESTIONNAIRES

#### 20. LIST OF QUESTIONNAIRES

Table 1. List of outcome measures

Outcome measure	Baseline	3	6	12
Demographic Factors: Age, sex, ethnicity, employment, education, marital status	✓			
Event type - stroke and pathological subtypes, or TIA and event date (physician diagnosed)	✓			
Hospitalization details: hospital, date of admission, date of discharge	✓			
Event details (revascularization and planned procedures) from medical records	✓			
Hospital Anxiety and Depression Scale	✓	✓	✓	✓
Stroke awareness (recognition of risk factors, knowledge of actions) [61]	✓	✓	✓	✓
Quality of life (EQ-5D-5L) [62]	✓		✓	
Cognitive functioning by MoCA [63]	✓		✓	
Medication adherence and self-efficacy (SEAMS) REF)	✓	✓	✓	✓
Physical measurements (non-fasting blood test, SBP/DBP, BMI, HR)*	✓		✓	
Absolute and relative 5-year risk of stroke (as measured by Stroke Riskometer app)	✓		✓	
Lifestyle factors (Diet score, physical activity, smoking, alcohol)	✓	✓	✓	✓
CVD outcomes, recurrent events, hospitalisation (stroke, CVD events) self-report and/or from clinical records	✓	✓	✓	✓
Health and Service costs: NMDS (NZ)			✓	✓
Productivity level NMDS (NZ)	✓	✓	✓	✓
Participant feedback questionnaire – Intervention group only	✓	✓	✓	✓

Items will include demographic factors, medical history, lifestyle risk factors, awareness of stroke risk factors, warning signs, symptoms and actions;[64] depression screening test (Hospital Anxiety and Depression Scale) health related quality of life ([EQ-5D-5L](#)),[62] health-care resource

use questionnaire, cognitive assessment (Montreal Cognitive Assessment MoCA) and participant satisfaction questionnaires. See 2 for details of measures collected at each timepoint. Life's Simple 7 score will be calculated from corresponding measurements of smoking, BMI, physical activity, healthy diet score, blood total cholesterol, glucose level and BP.[37]

Table 2. Life's Simple 7

Modifiable factors	Poor health	Intermediate health	Ideal health
Smoking status	Current smoker	Former ≤ 12 months	Never or quit > 12 months
Body mass index	≥ 30 kg/m 	25–29.9 kg/m 	< 25 kg/m 
Physical activity	No physical activity	1–3 times, less than 2.5 hours per week	≥ 4 times per week, 2.5 hours or more
Healthy diet score	0–1 component	2–3 components	4–5 components
Total cholesterol	≥ 240 mg/dL	200–239 mg/dL or treated to goal	< 200 mg/dL

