Data from the ARCOS V study on stroke risk factor prevalence and significance by age, sex and ethnicity, life satisfaction and other measures will guide the emphasis of the intervention on which particular health behaviours to focus on. As such, providing/referring to educational material is relevant to this model, including information booklets from the Heart and Stroke Foundation (<https://www.heartfoundation.org.nz/resources>) which include recommendations and guidelines on duration and frequency of exercise, weight loss, healthy eating, smoking cessation, and reducing alcohol intake,[88] and information about the free Stroke Riskometer mobile app (for stroke awareness and risk assessment, <https://nisan.aut.ac.nz/Stroke-Riskometer>). This is also in line with recent evidence recommending that RCT's for secondary disease prevention in TIA/minor stroke should include a combination of educational and behavioural interventions.[89-91]

---

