## 29. OUTCOME ASSESSMENTS (SEE TABLE 1 FOR THE FULL LIST OF OUTCOMES)

**Baseline:** The baseline assessment will be conducted prior to randomisation, and within 6 weeks of the index event. The Baseline assessment will be conducted in-person. The initial part of the assessment will be used to determine the full eligibility of the participant for the TIIPS trial. The full assessment will be completed for eligible participants only, and will include all measures required to analyse the primary and secondary outcomes

**3 months** (plus or minus 2 weeks from date of randomisation): The assessment will be conducted by telephone only, and will assess secondary outcomes.

**6 months** (primary outcome) (plus or minus 2 weeks from date of randomisation): The 6- month assessment be conducted in-person and will re-assess the primary outcome as well as secondary outcomes.

**9 months** (plus or minus 2 weeks from date of randomisation): The assessment will be conducted by telephone only, and will assess secondary outcomes.

**12 months** (plus or minus 2 weeks from date of randomisation): The assessment will be conducted by telephone only, and will assess secondary outcomes.

---

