### 34. INFERENCE ANALYSES

Intention to treat (ITT)[95] analyses and per protocol analysis will be used. To address the primary hypothesis ANCOVA will be used to compare the difference in systolic blood pressure at 6-months post randomisation between the HWC and usual care groups, accounting for baseline stratification factors: (age, gender and ethnicity), referral centres, geographical region and known influential clinical characteristics (e.g., comorbidities). To address the secondary hypotheses linear mixed effects (LME) repeated measures models will be used to investigate the differences in (1) adherence to medication (2) health-related quality of life (3) incidence of new vascular events including death (4) life satisfaction (5) cognition (6) mood) and (7) health service utilisation costs between the HWC and Usual care groups, and by ethnicity (sub-group analysis) at 6-months (plus

life-style and adherence at 1-year post-randomisation. These LMEs will model effect of time (baseline, 3-, 6- 9- and 12-months (medication adherence, lifestyle and awareness at only 12 months), post-randomisation whilst accounting for key demographic stratification factors known to confound with outcomes. Any data not collected within 6-weeks of the follow-up points will be classified as missing data. Baseline covariates of age, sex, most recent blood pressure measure and any additional variables predictive of outcome data will be included in the imputation model.[46] The reasons for missingness and the reasons will be recorded and accounted for. Sensitivity analyses will be conducted to test the assumptions of the model (including a complete case analysis in which only subjects with complete data are included). Familywise error control will be used to account for the multiplicity of tests. Inferences will be based on a 5% significance level and two-sided alternatives.

For the analysis of - CVD adverse outcomes (fatal and nonfatal stroke, TIA, myocardial infarction and heart failure, death attributable to CVD and all-cause mortality), we will use Kaplan-Meier life-test and estimate the hazard ratios (HR) and adjusted HR using time-to-event Cox regression analysis. Time to event analysis will include recurrent events and time-dependant variables where appropriate.

Competing risk method will also be applied to compare the CVD adverse outcomes between the two interventional groups, accounting for mortality outcome.

---

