## 40. APPENDIX C CASE RECORD FORMS

### List of TIIPS study case record forms

	Form Name	Purpose
1	Form A NHI number	Confidential record of NHI number
2	Form B Baseline and Screening	Screening for eligibility, and Baseline demographic and health related information
3	Form C Contact Details	Record of participant contact details, alternate contact and GP contact
4	Form F Follow-up	Follow-up assessments at 3, 6, 9 and 12 months
5	Form R Randomisation	Completion of data entry for randomisation, and record of group allocation
6	Form S Serious adverse events	Record of stroke/TIA/MI recurrent events, death and hospitalisation
7	Form Z Coaching assessment and compliance	Record of coaching sessions, compliance, and assessment of coaching quality

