**15G.1 Alcohol: Additional Section (Not a part of LS7 scoring)**

15G.1. Have you had anything alcoholic to drink in the last 12 months?  Yes  No

15G.2. If yes, total years of alcohol consumption.

\_\_\_\_\_

15G.3. Which of the following best describes how often you CURRENTLY drink alcohol?

Less than 1 drink a day (occasional)  
 1-2 drinks a day  
 3 or more drinks a day

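### The follow-up alcohol items cannot separate participants who stopped drinking after randomisation from occasional drinkers

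*Protocol*

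**What the plan says.** The alcohol block sits in Section 15 of Form B (screening and baseline) in Appendix C and is repeated unchanged on Form F (follow-up). Both forms label it as additional to LS7 scoring.

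- Item 15G.1 is a yes/no question: "15G.1. Have you had anything alcoholic to drink in the last 12 months".
- Item 15G.2 asks those who say yes for their total years of drinking.
- Item 15G.3 reads "15G.3. Which of the following best describes how often you CURRENTLY drink alcohol". It offers three answers: "Less than 1 drink a day (occasional"), one to two drinks a day, or three or more a day. None of the three means no drinking.

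The list of case record forms gives the purpose of Form F as "Follow-up assessments at 3, 6, 9 and 12 months". Table 1 (Section 20), the list of outcome measures, has a row "Lifestyle factors (Diet score, physical activity, smoking, alcohol"), ticked at baseline, 3, 6 and 12 months. The heading of Section 29 points to Table 1 for the complete set of outcomes. Section 24 describes the educational booklets that support coaching as covering, among other topics, "smoking cessation, and reducing alcohol intake".

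Alcohol is not named in the aims and secondary outcomes (Section 11) or in the secondary end points (Section 31). Section 34 refers only to lifestyle in general.

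**The concern.** A question suited to baseline has been carried to follow-up without changing its time frame. At baseline, a 12-month look-back describes the history a participant brings into the trial. At 3, 6 or 9 months it mixes time before randomisation with time after it, so a yes does not show whether the person has drunk since coaching began. The item that asks about the present could make up for this, but it has no zero.

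At stake is whether a listed outcome measure can record one of the clearest changes a participant could make. An answer that the form never offered cannot be recovered in the analysis, so a statistical analysis plan could not repair this.

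**Working it through.** No sample size, power or error-rate figure is involved, and the protocol gives no number to reproduce. The check compares the look-back with the date of randomisation, then asks which answers are open to someone who now drinks nothing.

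**Inputs**
- Look-back of 15G.1: 12 months, taken as 365 days (Form F).
- Visits at 3, 6, 9 and 12 months: about days 91, 183, 274 and 365 after randomisation.
- Visit window: two weeks either side. Section 29 gives it for the telephone visits as "plus or minus 2 weeks from date of randomisation): The assessment will be conducted by telephone only" and sets the same window for the 6-month visit in person.
- Analysis window (Section 34): "Any data not collected within 6-weeks of the follow-up points will be classified as missing data", that is 42 days.

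**Step 1. Start of the look-back relative to randomisation (day 0) = visit day − 365**

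| Visit | On time | With ±14 days |
|---|---|---|
| 3 months | 91 − 365 = −274 | −288 to −260 |
| 6 months | 183 − 365 = −182 | −196 to −168 |
| 9 months | 274 − 365 = −91 | −105 to −77 |
| 12 months | 365 − 365 = 0 | −14 to +14 |

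At 3, 6 and 9 months the look-back always starts at least 77 days before randomisation. Under the 42-day analysis window the latest start at 9 months is −91 + 42 = −49, still before randomisation. Anyone who drank at all after randomisation must answer yes at these visits.

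At 12 months, a participant who drank after randomisation can answer no only if the last drink fell within the first 14 days and the visit is correspondingly late. Under the analysis window that limit is 42 days.

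**Step 2. What 15G.3 offers a person who has stopped**

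After a yes on 15G.1, the only nearby answer is the lowest band. Under one drink a day means fewer than 1 × 7 = 7 drinks a week, so in whole drinks the band runs from 0 to about 6. Abstinence and regular light drinking share one code. Leaving the item blank is indistinguishable from missing data.

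**Step 3. What can still be recorded**

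Because 15G.3 asks about the present, these moves are visible at every visit:
- three or more a day to one to two a day;
- one to two a day to under one a day;
- three or more a day to under one a day.

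These changes are not visible:
- stopping, as such;
- any fall within the lowest band, including from occasional to none;
- any fall within the open-ended top band.

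**Step 4. Comparison with other items on the same form**

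The smoking item separates current smokers from those who quit within the past year. The physical activity item and several diet items offer a never answer. The health-service items include versions that ask about the time since the previous assessment. The alcohol block has none of these features.

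**The case against.** The strongest reply is that 15G.3 does its job. The only stated aim for alcohol is reducing intake; Section 24 uses the word cessation for smoking alone. A current-frequency item with three bands can show a reduction. Alcohol also carries little weight in this trial: it lies outside the LS7, is not a named end point, and has no between-arm comparison of its own. Table 1 also holds demographics and admission dates, so it works partly as a collection schedule.

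Most of this stands, and it rules out two stronger readings that a reader might infer.

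- **That the alcohol data cannot show the change coaching aims for, or must show no difference between arms.** The form contradicts this, because movement between bands is recordable. Suppose, purely as an assumption, that 10% of drinkers in the coaching arm and 2% in usual care stop by 6 months, a true difference of 10 − 2 = 8 percentage points. The difference recorded as a no on 15G.1 would be 0. But if a share p of those who stop, equal in both arms, began above the lowest band, 15G.3 would show 8 × p points of extra movement into that band: 0 if p = 0, 4 if p = 0.5, 8 if p = 1. The effect would be mislabelled as occasional drinking, but it would vanish only if p = 0.
- **That most participants start in the lowest band, where no improvement can show.** Section 12 excludes past-year alcohol abuse, which makes a concentration at the low end possible. It does not exclude people who have one to two drinks a day, and the protocol gives no baseline distribution.

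The reply does not remove the narrow defect. A participant who has stopped has no correct answer on 15G.3, whether stopping is the aim or one way of reaching it.

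**Conclusion.** The point holds in a limited form and has low weight. On Form F, a participant who drinks after randomisation and then stops cannot be recorded as a non-drinker at 3, 6 or 9 months. At 12 months this is possible only in the narrow late-visit case above. Such a person is coded with occasional drinkers or looks like missing data.

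The size of the loss cannot be computed. It depends on how many participants stop and on the band they start from, and the protocol gives neither. The primary end point (systolic blood pressure), the LS7 score and the power calculation are untouched.

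The conclusion assumes that the items are answered as printed and that the database has no unprinted answer or skip rule that would capture current non-drinkers.

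**What to change.** 1. On Forms B and F, add a none answer to 15G.3, giving four levels instead of three.
2. On Form F, reword 15G.1 to cover a period after randomisation, for example the time since the previous assessment, as some health-service items on that form already do. Baseline is completed just before randomisation, so this also works at 3 months.
3. Keep the 12-month question on Form B, where it describes history.

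The none answer identifies a current non-drinker at any visit. The reworded 15G.1 confirms it once a full interval has passed without drinking. Falls within the top band would still not be recorded.

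The cost is three item edits in REDCap (15G.3 on two forms, 15G.1 on one), with no extra visit and no added question. The downside is that responses already collected under the old wording stay coarser and are not fully comparable with the new ones. The date of the change should be recorded. Where old and new responses are pooled, none and the lowest band can be merged, assuming that earlier non-drinkers ticked the lowest band rather than leaving the item blank.

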### Part H: Diet

15H.1. How many portions of fresh fruit and vegetables do you eat per day on average?

---

Note: 1 portion = 1 pc of fruit, or 1 cup of vegetables e.g., 1 apple and 1 cup of mixed salad= 2 portions.

15H.2. LS7 healthy diet component met? Tick if more than 4 portions per day

- Yes  No

15H.3. How many times per week do you eat fish (100g or more) including canned or frozen fish?

---

15H.4. LS7 healthy diet component met? Tick if more than 2 servings per week

- Yes  No

15H.5. Do you add salt to your food AFTER it has been cooked?

- Yes  No

15H.6. How often do you eat highly processed foods (such as sausages, ham, chips, crisps etc) and/or fast food/takeaways per week?

- Never  
 Less than once per week  
 1-2 times per week  
 3+ times per week

15H.7. LS7 healthy diet component met?

- Yes  No

Note: Tick if NEVER or LESS than once per week.

15H.8. During the past month, how often did you eat sweets/chocolates etc or drink fruit juices, soft drinks or energy drinks?

- Never  
 Less than once per week  
 1-2 times per week  
 3+ times per week

(Note: Do not include diet varieties. Soft drinks are often carbonated/ fizzy and include Coca-Cola, Pepsi, lemonade, ginger beer, energy drinks (Red Bull, Lift plus), Powerade, E2, G-force. Excludes diet varieties, flavoured waters, and sports waters. )

15H. 9. LS7 healthy diet component met? Tick if less than 3 times per week

- Yes    No

15H.10. How often would you have 100g of whole grains (e.g., wholegrain cereal, millet, buckwheat, rye, brown rice, quinoa, rolled oats, 3 slices of wholegrain bread, beans, dhal etc) per day?

- Never  
 Less than once per week  
 1-2 times per week  
 3+ times per week

15H.11. LS7 healthy diet component met?

- Yes    No

Note: Tick if less than 3 times per week

15H.12. LS7 Healthy Diet score

- if 4 to 5 components are ticked.  
 if 2 to 3 components are ticked  
 if 0-1 components are ticked

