As well as improving blood pressure, a key secondary aim of the trial is to address multifactorial modifiable risk factors as a way to lower the risk of stroke and CVD. The INTERSTROKE study also found that overall there were ten potentially modifiable risk factors are collectively associated with about 90% of the population-attributable risk of stroke.[30] including lifestyle related risk factors such as physical activity, diet, and smoking. The Life's Simple 7 (LS7) was developed by the American Heart Association, (AHA), to predict ideal cardiovascular health using seven domains or metrics.[37-39] These are; blood pressure, cholesterol, glucose, body mass index, smoking, physical activity, and diet.[37] The LS7 is a simple scoring system to assess cardiovascular health with scores ranging from 0 to 14, with the overall LS7 score categorised as inadequate (0–4), average (5–9), or optimum (10–14) cardiovascular health (see Table 1). Inadequate and average scores on the LS7 have a high association with increased CVD/stroke risk and mortality.[38] Ideal levels of the Life's Simple 7 factors are defined as: non-smoker or quit >1 year ago; body mass index (BMI) of <25 kg/m^2; ≥150 min/week of moderate+vigorous physical activity; 4 to 5 components of a healthy diet pattern; untreated total cholesterol of <5.2 mmol/L; untreated blood pressure of <120/80 mm Hg; and untreated fasting glucose of <5.6 mmol/L. The Reasons for Geographic and Racial Differences in Stroke study (REGARDS) found that in 22,914 people with no previous history of CVD, an improvement by one category (from inadequate to average or average to optimum) or of the LS7 score was associated with a 25% lower risk of stroke, and that a 1-point higher LS7 score was associated with an 8% lower risk of stroke.[37] In the Atherosclerosis Risk in Communities (ARIC) study of 1277 individuals who experienced a MI, adverse outcomes were inversely related to mid-life LS7 scores using the LS7 scoring where two-points are given for each optimum domain.[40] A recent review suggested that “an integrated socio-behavioural and medical intervention to improve LS7 factors was a potent and likely cost-effective approach to cardiovascular and general health promotion and disease prevention”.[41]

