## The Life's Simple 7 scale

Table 3. Definitions of the LS7 categories \*

Life's Simple 7	Level of Cardiovascular Health		
	Poor	Intermediate	Ideal
Lifestyle Factors			
Body mass index, kg/m 	≥30	25.0–29.9	<25
Physical activity, min/day	0 MVPA	>0 – <150 MPA or MVPA >0 to <75 VPA	≥150 MPA or MVPA ≥75 VPA
Healthy diet score	0–1 components	2–3 components	4–5 components
Cigarette smoking	Current	Quit <12 months ago	Never or quit >12 mo
Medical risk factors			
Blood pressure, mmHg	≥140/≥80	120 – 139/80–89 or <120/<90 with med	<120/<80 no med
Total cholesterol, mg/dL	≥240	200–239 or <200 with medication	<200
Fasting blood glucose, mg/dL	≥126	100–125	<100
Glycosylated Hemoglobin, %	≥6.5 or taking diabetes med	5.7–6.4	<5.7

M, moderate; V, vigorous; PA, physical activity.

(i) Fruits and vegetables ≥4.5 cups/day; (ii) Fish 3.5-oz servings (preferably oily fish) ≥2 servings/week; (iii) Sodium <1500 mg/day; (iv) Sweets/sugar-sweetened beverages ≤450 kcal (36 oz)/week; (v) Whole grains (1.1 g of fiber in 10 g of carbohydrates), 1-oz-equivalent servings ≥3 servings/day.

\*Note: Fasting blood glucose in mmol/l is ≥7.00 (poor), 5.55–6.99 (adequate) and <5.55 (optimum). Plasma total cholesterol, mmol/l ≥ 6.22 (poor), 5.18–6.21 (adequate) < 5.18 (optimum).

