## 31. SECONDARY END POINTS

Secondary outcomes include: (1) difference in the mean change in the LS7 scale score at 6 months post-randomisation between UC and HWC (2) the change in individual lifestyle components of the LS7 scale (BMI, smoking, physical activity, and diet) at 6 and 12 months; (3) diastolic BP (mmHg); (4) quality of life (EQ-5D-5L), (5) awareness of stroke risk factors and warning signs, (6) medication adherence (7) cognitive outcomes (8) adverse events including hospitalisations; and (9) health service use and costs.

The LS7 scale includes BP, cholesterol, blood glucose, BMI, smoking, physical activity, and diet. The score of LS7 will be calculated by providing 2 points for ideal, 1 point for intermediate, and 0

points for poor status of each of the 7 individual factors. Ideal levels of health factors were: non-smoker or quit >1 year ago; BMI <25 kg/m^2; BP <120/80 mm Hg; total cholesterol <200 mg/dL; fasting blood glucose <100 mg/dL; ≥150 min/week of physical activity; and a healthy diet score (≥4 components). Study participants who were treated to target levels for hypercholesterolemia, hypertension, or diabetes mellitus were classified as intermediate for the respective health factor. Thus, the LS7 summary score will range from 0 to a maximum of 14 points, with a higher score indicating healthier status.

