### Measurement of blood sugar and lipids

Non-fasting blood test will be performed using certified Cardiochek PA Analyser (Figure). Cardiochek point of care system allows determination of the full lipid panel within 2 minutes.

Medication should not be stopped

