### Section 10: Current Medications.

10.2. CVD Medications prescribed at discharge (Tick all that apply)

- Aspirin  
 Dipyridamole  
 Clopidogrel  
 Warfarin  
 Dabigatran  
 Rivaroxaban  
 Blood pressure lowering medication(s)  
 Lipid lowering therapy (statins)  
 Diabetes medication(s),  
 Mood modification therapy  
 Oral contraceptives  
 Supplements (herbal or vitamins)  
 Other  
 None of the above  
 (Complete Section 11 only if medications medications are taken (Q10.1))

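### Item 15H.11 on Forms B and F scores whole grains in reverse, so a coaching gain in whole-grain intake lowers the LS7 secondary end point

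*Protocol*

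**What the plan says.** LS7 is built from seven factors scored 0, 1 or 2, giving a maximum of 14 (section 31). The diet factor counts five components: 0–1 met scores 0, 2–3 scores 1, and 4–5 scores 2. Change in LS7 at 6 months is secondary end point (1) in section 31 and secondary aim 1 in section 11.

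Note (v) under Table 3 defines the whole-grain component as "1-oz-equivalent servings ≥3 servings/day". On Forms B and F (Appendix C, Section 15, Part H), item 15H.11 says "Note: Tick if less than 3 times per week". The sweets and sugary-drinks item, 15H.9, has the same rule: "LS7 healthy diet component met? Tick if less than 3 times per week". Item 15H.10, which feeds 15H.11, asks about 100 g of whole grains per day but offers only weekly frequencies, the highest being three or more times per week.

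Other LS7 entries also disagree:

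- **Fish.** Item 15H.4 requires more than 2 servings a week; Table 3 requires at least 2.
- **Activity.** Table 3 labels the row "Physical activity, min/day" with a cut-off of 150. Section 4 has "≥150 min/week of moderate+vigorous physical activity", and section 31, Table 2 and the forms are also weekly.
- **Diastolic pressure.** Table 3 rates 80 and above as poor while also listing 80–89 as intermediate. Table 2 starts poor at 90.
- **Glucose.** Appendix A says "Non-fasting blood test will be performed using certified Cardiochek PA Analyser", while section 31 defines ideal as "fasting blood glucose <100 mg/dL". No non-fasting cut-off is given.
- **Medication.** Form F, item 10.2, reads "CVD Medications prescribed at discharge (Tick all that apply", although treatment status helps decide the intermediate category.

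**The concern.** A less-than rule suits a food to be limited, such as sweets. Applied to a food to be encouraged, it reverses the component. The identical wording suggests that the rule was carried over from 15H.9.

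The direction matters because the intervention covers healthy eating: section 24 says coaching participants are given or referred to material on it. If that raises whole-grain intake more in the coaching arm, the scoring error differs between arms and works against coaching. The diet score, total LS7 and the change in LS7 risk category inherit it. The economic evaluation would too, if it uses LS7, which it names as one of two example inputs.

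**Working it through.** **Inputs.** Diet bands and points are from the forms, Table 3 and section 31. The printed rule is from 15H.11. The earlier trial's LS7 means are from section 6.

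**Check of the plan's figure.** 7 factors × 2 points = 14, as stated.

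**Effect on one participant.** Let k be the number of the other four diet components met. Compare the printed rule with the same three-times-a-week cut in the right direction.

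| k | Eats whole grains 3+ times/week: right → printed | Eats them less often: right → printed |
|---|---|---|
| 0 | 0 → 0 | 0 → 0 |
| 1 | 1 → 0 | 0 → 1 |
| 2 | 1 → 1 | 1 → 1 |
| 3 | 2 → 1 | 1 → 2 |
| 4 | 2 → 2 | 2 → 2 |

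The printed rule is wrong by exactly 1 LS7 point when k = 1 or k = 3, and harmless otherwise.

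**Effect on the between-arm difference.** Assumptions, none of them in the protocol: each of the other components is met independently with probability q between 0.2 and 0.7; k does not change; and coaching raises the share eating whole grains 3+ times a week by d = 0.10 to 0.30 relative to usual care.

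P(k = 1 or 3) = 4q(1−q)³ + 4q³(1−q)

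- q = 0.2: 0.4096 + 0.0256 = 0.435
- q = 0.5: 0.25 + 0.25 = 0.500 (the maximum)
- q = 0.7: 0.0756 + 0.4116 = 0.487

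True contribution to the LS7 difference = d × P; recorded contribution = −d × P.

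- Smallest: 0.10 × 0.435 = 0.044, recorded as −0.044
- Largest: 0.30 × 0.500 = 0.150, recorded as −0.150

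**Scale.** The earlier trial's difference in LS7 change was (7.39 − 7.08) − (7.15 − 7.15) = 0.31.

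**Limit of the comparison.** Table 3's threshold is daily. Someone eating whole grains three or more times a week but not daily fails Table 3 and is also left unticked by the printed rule, so the form is right for that person by accident. The weekly options cannot separate this group from daily eaters.

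**Portion size.** 100 g is about 3.5 oz (Part H and Table 3 use these interchangeably for fish). One 15H.10 portion is therefore already about three one-ounce servings. Three such portions a day would be about 300 g, roughly three times the Table 3 definition.

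**Activity label.** Read literally, 150 min/day × 7 = 1,050 min/week, or 17.5 hours, against 2.5 hours elsewhere.

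**The case against.** The strongest reply is that the damage is bounded and partly reversible. The primary end point is systolic pressure in mmHg and does not use LS7. The whole-grain error works against coaching, so on this item it does not favour a false positive. The raw 15H.10 answers are recorded, so the direction can be corrected at analysis. All of this stands. It does not excuse an instruction that contradicts the protocol's own definition, and re-scoring cannot recover a daily threshold from weekly answers.

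A reader might also infer that activity, blood pressure and glucose are mis-scored to a similar degree. The documents do not support that:

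- The min/day label and the diastolic overlap are slips in Table 3. They affect scores only if that table is programmed literally. The form collects activity as hours per week, cut at 2.5, and prints no blood-pressure cut-offs.
- The glucose mismatch is real, but it should fall on both arms alike, adding noise rather than a clear direction.
- The medication point is uncertain. The Form F section is headed as current medications, and its skip note refers to an item 10.1 that is not shown, so a current-use question may exist.

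**Conclusion.** The whole-grain rule is reversed on both forms and should be corrected. It is the one inconsistency here with a clear direction against the intervention. Under the stated assumptions, a true gain of about 0.04 to 0.15 LS7 points would be recorded as an equal loss, provided staff or the database follow the printed note.

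It is tempting to express this as a fixed share of the expected treatment effect. The protocol gives no whole-grain intake or expected dietary shift, and 0.31 is a 9-month result in people without prior stroke or TIA. It serves for scale only.

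The fish, activity and diastolic points are consistency corrections. Glucose needs a stated scoring rule, and the medication item needs clarifying.

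**What to change.** 1. **Whole grains, Forms B and F.** Reverse 15H.11 and make 15H.10 consistent with Table 3. Either count one-ounce servings per day and tick at three or more, or keep the 100 g portion and tick if it is eaten at least daily.
2. **Completed records.** Re-score from the stored 15H.10 answers, taking three or more times per week as the nearest available category to met. Report that the daily threshold cannot be recovered, so some people who eat whole grains less than daily will be counted as met.
3. **Fish.** Set 15H.4 to at least 2 servings a week; past records can be recomputed from the count in 15H.3.
4. **Table 3.** Reconcile it with Table 2 and section 31: activity in minutes per week, and no overlap in the diastolic categories.
5. **Glucose.** Keep it in the main LS7 score and pre-specify LS7 without glucose (six factors, 0–12) as a sensitivity analysis. Scoring only fasting samples would leave most LS7 totals missing, because sampling is non-fasting by design.
6. **Medication.** If Form F item 10.2 feeds the treated-to-goal category, make clear that it records medication taken at the time of the visit.

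The cost is small: wording and calculation edits in REDCap, Table 3 corrections, one re-scoring of existing records and one added sensitivity analysis. Early correction matters because each further record collected on the weekly options lacks the daily threshold.
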